8.3.2 Tumor Marker Evaluation (Part 1 and Part 2 Basket Cohort)

To include tumor markers that are part of the trial site standard practices as indicated by tumor type, if applicable.

It is recommended that tumor markers are evaluated at timepoints coinciding with the CT/MRI imaging studies as listed in Section [8.3.1](#).

8.3.3 Archival Tumor Tissue for *MET* and *KRAS* Assessment (Part 1 and Part 2 Basket Cohort)

To be assessed locally. Does not need to be repeated if *MET*-amplification and *KRAS* mutational status have been assessed previously and the pathology report is available to document findings. May be performed as part of prescreening outside the 14-day screening period, provided separate informed consent has been obtained.

- Screening

- Part 1: Eligibility assessment for *KRAS* mutational status will be done using archival tumor tissue, whenever possible. If archival tissue is not available, tissue from a tumor biopsy performed during screening will be used.

Assessment of *MET*-amplification status is not required, but tissue should be assessed if feasible.

- Part 2:

Eligibility assessment for *KRAS* mutational status may be done using archival tumor tissue. If archival tissue is not available, tissue from the tumor biopsy performed during screening will be used. Refer to Section 8.3.4.

It is preferred that the eligibility assessment for *MET*-amplification be done using tissue from a tumor biopsy performed during screening, however archival tumor tissue may be used at the investigator's discretion.

Note: If a new biopsy is performed for *MET*-amplification testing, tissue from this biopsy may be used for *KRAS* mutation testing as well.

During Part 2 ONLY, peripheral blood collection for *KRAS*-mutation assessment and for *MET*-amplification assessment in ctDNA is allowed as a local pre-screening methodology by Guardant360 analysis. Other liquid biopsy methodologies, except if used to detect *MET*^{Ex14Del}, will only be allowed if previously approved by the Sponsor. Subsequent required tumor tissue evaluation to confirm *MET*-amplification must meet the protocol-specified inclusion criteria.

NSCLC *MET*^{Ex14Del} Cohort (pre-protocol v8.0): Eligibility assessment for *MET*^{Ex14Del} status will be done according to local institutional standards. Assessment in ctDNA by Guardant360 technology or equivalent is allowed. Subsequent confirmation in tumor tissue is preferred but not required, however, archival tissue to be submitted, if available (applies only to patients with *MET*^{Ex14Del} tumors entered prior to suspension of the Basket Cohort and establishment of NSCLC *MET*^{Ex14Del} Cohort).

8.3.4 Tumor Biopsy for Eligibility Assessment and Biomarker Analysis (Part 1 and Part 2 Basket Cohort)

To be assessed locally for eligibility:

- Screening; Part 1 and Part 2, if applicable as per Section 8.3.3 (i.e., Basket Cohort)

Note: It will be permissible to perform this procedure outside the 14-day screening period, provided informed consent for the trial has been obtained

To be assessed centrally for biomarker analysis:

- Screening
 - Part 1: Optional; only applicable for patients with known *MET*-amplification who consent to this optional procedure; to be performed after confirmation of eligibility
 - Part 2:

Basket Cohort: Required, if archival tissue is unavailable or insufficient for central analysis; to be performed after confirmation of eligibility

Note: Tissue from a tumor biopsy performed during screening is preferred, however archival tissue may be submitted for central analysis at the Investigator's discretion, provided the archival tissue is suitable as specified in the laboratory manual. It must be ensured that the archival tissue can be made available to the central laboratory prior to deciding to omit the tumor biopsy procedure at time of screening

NSCLC MET^{Ex14Del} Cohort: Optional

- Post-dosing

If feasible, it is preferred that the second biopsy is taken from the same tumor site from which the first biopsy was taken.

- Part 1: Optional; only applicable for patients with known *MET*-amplification who consent specifically to this optional procedure; to be performed as specified below for Part 2 patients

- Part 2:

Basket Cohort: Required; EOC2 (i.e., coinciding with time of first response assessment) or upon PD, whichever occurs first

Note: EOC assessments may be performed at any time during the week prior to Day 1 of the next cycle, including Day 1 of the next cycle, prior to dosing

NSCLC MET^{Ex14Del} Cohort: Optional, at the timepoint specified above

8.3.5 Tumor Biopsy for *MET* Status and Biomarker Analysis (Part 2 NSCLC *MET*-Amplified Cohort and NSCLC *MET^{Ex14Del}* Cohort)

To be assessed centrally:

- Screening (Mandatory)

Note: It will be permissible to perform this procedure outside the 14-day screening period, provided informed consent for the trial has been obtained

- **NSCLC MET-Amplified Cohort**: Required; tissue from a newly performed pre-dosing tumor biopsy must be submitted for central confirmation of *MET*-amplification

(Patients may be entered and treated based on local assessment of a recent tumor biopsy [if available and performed outside of the screening process as part of the site's usual practice] provided no intervening antineoplastic therapy has been administered; otherwise tissue from a newly performed biopsy must be obtained and submitted)

- **NSCLC MET^{Ex14Del} Cohort**: Required; tissue from a recent or newly performed pre-dosing tumor biopsy must be submitted for central assessment of *MET^{Ex14Del}*

(Patients may be entered and treated based on local institutional standards; alternatively, assessment in ctDNA by Guardant360 technology or equivalent is allowed; a recent [as defined above] or newly performed pre-dosing biopsy must still be submitted)

- Post-dosing (Optional)

EOC2 (i.e., coinciding with time of first response assessment) or upon PD, whichever occurs first

Note: EOC assessments may be performed at any time during the week prior to Day 1 of the next cycle, including Day 1 of the next cycle, prior to dosing

To include a tumor biopsy performed by a core biopsy of a locally recurrent or metastatic lesion. This procedure will take place prior to the first Sym015 administration. The tumor biopsy must be performed with minimal morbidity to the patient by a percutaneous core needle biopsy either with or without the aid of an imaging modality chosen at the discretion of the physician performing the biopsy.

Biopsy specimens will be obtained using standard sterile surgical techniques and formalin-fixed, paraffin-embedded according to standard laboratory techniques. All tumor tissue samples should be reviewed by a pathologist to confirm the presence of tumor cells before the tissue sample (blocks or slides) is sent to the central laboratory for analysis. A detailed laboratory manual specifying sample collection, handling, storage, and shipment will be provided to the trial sites.

Analysis of tumor biopsies may include genes and/or proteins that are unknown or have not been included in the scientific hypotheses of this trial, but that, during the collection of data from this trial, may evolve as new candidate genes and markers related to Sym015 safety, efficacy, or mechanism of action.

All analyses will be related to and used only in connection with the data collected in the present trial and future development of Sym015, and the identity of the patient will remain confidential. The analyses will not have any medical consequences for the patient or their relatives.

Tumor biopsy samples will be stored for up to 15 years after completion of the trial, where after all samples will be destroyed.

8.4 Pharmacokinetic Assessments

PK samples will be taken according to the schedules shown in [Table 9](#).

Analysis of PK will be performed at a central laboratory. A detailed laboratory manual specifying sample collection, handling, storage, and shipment will be provided to the trial sites.

In the event that a collected serum sample is inadequate or insufficient for PK analysis, the analysis of PK can be done using an anti-drug antibody (ADA) serum sample from the same time point, if available.

Note: Comprehensive collection of clinical samples is critical to the conduct of this study. In situations where collection of EOI + 8h samples is logically difficult due to clinic staff availability, the observation period may be shortened and an "end of day" sample may be obtained at the latest practical time. Such an option (if to be routinely employed) is available only after previous discussion with and approval by the Sponsor.

Table 9 Schedule of Pharmacokinetic Assessments

		Cycle 1			Cycles Thereafter		EOT	IM FUP
Sampling Time	Window	D1-D3	D8	D15	D1	D15		
Part 1 / Part 2 Basket Cohort								
Prior to SOI	- 4 h	X		X ¹	X ¹	X ¹		
EOI	+ 10 min	X		X ¹	X ¹	X ¹		
EOI + 1 h	±15 min	X						
EOI + 2 h	±30 min	X						
EOI + 4 h	±30 min	X						
EOI + 8 h	±90 min	X						
EOI + 24 h	±6 h	X						
EOI + 48 h	±12 h	X						
During Visit	NA		X				X	X
Part 2 NSCLC Cohorts (effective with protocol v8.0; December 2018)								
Prior to SOI	- 4 h	X		X ¹	X ¹	X ¹		
EOI	+ 10 min	X		X ¹	X ¹	X ¹		
EOI + 4 h	±30 min	X						
EOI + 48 h	±12 h	X						
During Visit	NA		X				X	X

Abbreviations (in alphabetical order): D, day; EOI, End of Infusion, EOT, End of Treatment Visit; NA, Not Applicable; h, hour; min, minutes; 1M FUP, 1-Month Follow-up Visit; SOI, Start of Infusion

1) If Sym015 is paused, only one PK sample should be taken during the visit

8.5 Anti-Drug Antibody Testing

To assess formation of ADA. All samples must be taken prior to the Sym015 infusion of that visit. Analysis of ADA and residual serum levels of Sym015 will be performed at a central laboratory. A detailed laboratory manual specifying sample collection, handling, storage, and shipment will be provided to the trial sites. In the event that a collected serum sample is inadequate or insufficient for ADA analysis, the analysis of ADA can be done using a PK serum sample from the same time point, if available.

- C1/D1
- C2/D1 (Part 2 only)
- Day 1 of to every second cycle thereafter, i.e., Cycle 3, 5, 7 etc. (prior to dosing)
- EOT
- 1M FUP

8.6 Skin Biopsy (Part 1 only)

To be performed only after eligibility has been confirmed

Analysis of skin biopsy samples will be performed at a central laboratory. Biopsy specimens will be obtained using standard techniques and formalin-fixed, paraffin-embedded according to standard laboratory techniques. A detailed laboratory manual specifying sample collection, handling, storage, and shipment will be provided to trial sites.

Skin biopsies are requested from a rash-free area.

- Screening, after confirmation of eligibility
- EOC2 (i.e., coinciding with time of first response assessment) or upon PD, whichever occurs first

Note: EOC assessments may be performed at any time during the week prior to Day 1 of the next cycle, including Day 1 of the next cycle, prior to dosing

8.7 Blood Sample for Genomic and Biomarker Analyses

To include assessment of *MET*-amplification and *MET*^{Ex14Del} status; analysis of all samples taken will be performed at a central laboratory. A detailed laboratory manual specifying sample collection, handling, storage, and shipment will be provided to the trial sites.

- Screening (it will be permissible to perform this procedure outside the 14-day screening period, provided informed consent for the trial has been obtained)
- EOC2 (coinciding with time of first response assessment or upon PD, whichever occurs first)

Note: EOC assessments may be performed at any time during the week prior to Day 1 of the next cycle, including Day 1 of the next cycle, prior to dosing

- EOT (if after EOC2; need not repeat if patient is discontinuing at the EOC2 or if a sample was obtained upon PD)

Note: If a tumor biopsy is collected at the same time point as the biomarker blood sample, the biomarker blood sample should be collected prior to collecting the tumor biopsy.

The purpose of the pharmacodynamic biomarker assessments is to develop an approach for the identification and validation of genes or proteins that may predict which patients are likely to respond to Sym015, and that may change with the possible development of acquired resistance to Sym015. Potential biomarkers of interest include genes, gene transcripts and proteins of the RTKs and molecules of the MET signaling pathway, including MET, HGF, EGFR, HER2, HER3, IGF1R, ROS1, RET, PIK3CA, PTEN, cMYC, KRAS, NRAS, BRAF, AKT1, FGFR, and RON.

Analysis of biomarker blood samples may include genes and/or proteins that are unknown or have not been included in the scientific hypotheses of this trial, but that, during the collection of data from this trial, may evolve as new candidate genes and markers related to Sym015 safety, efficacy, or mechanism of action.

All analyses will be related to and used only in connection with the data collected in the present trial and future development of Sym015, and the identity of the patient will remain confidential. The analyses will not have any medical consequences for the patient or their relatives.

Biomarker samples will be stored for up to 15 years after completion of the trial, where after all samples will be destroyed.

8.8 Handling of Biological Samples

All biological samples to be analyzed locally will be collected and handled according to institutional practices.

All biological samples to be analyzed centrally will be collected and handled according to a detailed laboratory manual.

Retention time for biologic specimens will be specified in the laboratory manual.

8.9 Follow-up Assessments

Assessments at the 1M FUP Visit include disease status and subsequent cancer therapy.

After the 1M FUP Visit, the Investigator will make every effort to obtain follow-up information on response assessment and/or OS every 2 months. Response assessment follow-up is required in the event of an ongoing SD, PR or CR, as per RECIST v1.1 at the 1M FUP Visit, until PD or another therapeutic intervention is initiated. Survival follow-up is required until death, withdrawal of consent, or termination of the trial. This continued follow-up does not require an in-person visit at the trial site, but may be obtained by collection of data/documentation.

8.10 Appropriateness of Measurements

Standardized methods for assessments of efficacy and safety variables will be used.

9. ADVERSE EVENTS

9.1 Definitions of Adverse Events

9.1.1 Adverse Event

An AE is any untoward medical occurrence in a patient or a clinical investigation subject administered a pharmaceutical product, and which does not necessarily have a causal relationship with this treatment. An AE can therefore be any unfavorable and unintended sign (including an abnormal laboratory finding), symptom, or disease temporally associated with the use of an IMP, whether or not considered related to the IMP.

Causality for the above-mentioned AE will be assessed appropriately as: Related to IMP, Possibly Related to IMP, Probably Related to IMP, Unlikely Related to IMP, or Not Related to IMP. In addition, any AE, regardless of causality, that also meets the seriousness criteria, will be reported on an SAE form.

9.1.2 Events Not to be Considered as Adverse Events

A pre-existing condition (i.e., a disorder that is present before the AE recording period starts and is noted on the medical history/physical examination form) should not be recorded as an AE unless the condition worsens, or episodes increase in frequency during the AE recording period.

PD will not be captured as an AE unless the nature of the PD is different than expected (i.e., other diagnosis and/or signs/symptoms that are not typical of PD).

Note: PD may be reported as an AE in the case of patient death, with death being the outcome of the event.

An abnormal laboratory value or an abnormality in physiological testing (such as ECGs) need not be reported as an AE unless one of the following applies:

- The Investigator considers the abnormality clinically significant
- The event meets the definition of an SAE
- The event requires an intervention
- The event results in an action taken with Sym015 (dose-reduction and/or withdrawal)

Diagnostic and therapeutic non-invasive and invasive procedures, such as surgery, should not be recorded as AEs. A medical condition for which an unscheduled procedure was performed, should however be recorded if it meets the definition of an AE. For example, an acute appendicitis should be recorded as the AE and not the appendectomy.

Procedures to support the treatment regimens, such as insertion of central venous catheters, etc. should not be recorded as AEs, unless the procedures result in complications.

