7.1.4.2 Dose-Delays for Sym015-Related or Disease-Related Toxicities

Clinical judgment will be used when determining whether it is advisable to continue a patient on to the next dosing. In order to dose a patient, the following criteria must be met:

- ANC $> 1.0 \times 10^9/L$ (1000/mm³)
- Platelet count $> 60 \times 10^9/L$ (60,000/mm³)
- Any ongoing AEs should NOT meet the criteria for DLT, during the DLT observation period
- Any ongoing AEs, assessed as possibly, probably, or related to Sym015, should have either ameliorated to \leq Grade 1 severity, returned to baseline status, or resolved with the exception of Grade 2 clinical events that are being adequately controlled with best supportive care (e.g., nausea, vomiting, diarrhea, fatigue) and asymptomatic laboratory abnormalities that are considered clinically insignificant or that are resolving with medical therapy

Should any one of the criteria above not be met, dosing of Sym015 must be delayed until the patient meets the above criteria. All per protocol assessments must be done.

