9.1.4 Serious Adverse Events

An SAE is an AE that meets one or more of the following outcome criteria:

- Results in death

Note: In the case of deaths, the event(s) leading to the death should be recorded and reported as SAE(s) with the outcome "Fatal". The death itself will not be reported as an event (SAE), unless the cause of the death is unknown (e.g., in case of unexplained or sudden death)

- Is life-threatening

Note: The term "life-threatening" in this definition refers to an event in which the patient is at immediate risk of death at the time of the event; it does not refer to an event which hypothetically might cause death if it was more severe

- Requires inpatient hospitalization or prolongation of existing hospitalization
- Results in persistent or significant disability/incapacity
- Is a congenital anomaly/birth defect
- Is medically important

Note: Medical and scientific judgment must be exercised in deciding whether an AE is believed to be "medically important". Medically important events may not be immediately life-threatening or result in death or hospitalization but may jeopardize the patient or may require intervention to prevent one of the other outcomes listed in the definition above

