9.1.5 Events that Do Not Meet the Definition of Serious Adverse Events

PD will not be captured as an SAE unless the nature of the PD is different than expected (i.e., other diagnosis and/or signs/symptoms that are not typical of PD).

Note: PD may be reported as an SAE in the case of patient death, with death being the outcome of the event.

Elective surgery or other scheduled hospitalization periods that were planned before the patient was included in this trial are not to be recorded as SAEs, unless an outcome is considered serious.

Hospitalization for observation or convenience following the Sym015 infusions without an SAE occurring should not be recorded as an SAE, e.g., if a patient is hospitalized merely for

observation, or if a patient finalizes the infusion at a time of day requiring a convenience overnight stay in the hospital.

If procedures to support the treatment regimens require hospitalization, they should not be recorded as SAEs. However, in cases where a procedure results in complications requiring/prolonging hospitalization, this must be recorded and reported as an SAE.

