10.5.3 Safety Endpoints and Analyses

The safety endpoints are presented below. These endpoints will all be presented for the FAS by trial part. Safety data will be summarized using descriptive statistics and frequency distributions as appropriate.

In Part 1 and Part 2 of the trial, the following safety endpoints will be assessed:

- Nature, incidence and severity of AEs measured from baseline to end of trial participation
- AEs leading to dose-reductions, dose delays and permanent treatment cessation
- Changes in safety laboratory values from baseline to end of trial participation
- Changes in vital signs and physical examinations from baseline to end of trial participation
- Occurrence of ADAs to Sym015 measured in serum at selected timepoints from baseline to end of trial participation

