10.5.3.1 Adverse Events

The AEs will be coded using Medical Dictionary for Regulatory Activities (MedDRA) current version. AEs will be regarded as treatment emergent AEs (TEAEs) if they occur after first treatment. Non-treatment emergent AEs (non-TEAEs) are defined as AEs collected before dosing. TEAEs will be presented by SOC and Preferred Term unless stated otherwise. The frequencies of TEAEs will be presented including number and percentages of patients having experienced an event and the total number of events.

AEs including SAEs are reported from signing of the informed consent for participation in the trial and until the end of trial participation. SAEs reported outside the required reporting window are only entered into the safety database and will be described separately in the report.

Note: Patients who sign informed consent and are subsequently deemed to be screening failures will be followed for the occurrence of SAEs/AEs until it is determined that they will not be participating in the trial.

All AEs will be listed. The TEAEs will be presented using summary tables by trial phase including:

- AEs, in total and sorted by frequency
- AEs by relationship
- AEs by CTCAE Grade and maximum CTCAE Grade

- SAEs, in total, and by relationship
- AEs leading to withdrawal from treatment
- AEs leading to trial drug-interruption or dose-reduction
- Fatal AEs

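### Section 9.1.2 does not name dose delay among the treatment actions that make a laboratory abnormality an AE, so the outputs on AEs leading to delay or interruption can under-count laboratory-driven delays

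*Protocol*

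**What the plan says.** **When a laboratory value becomes an AE.** Under Protocol 9.1.2 an abnormal laboratory value "need not be reported as an AE unless one of the following applies". There are four conditions:

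- investigator judgment ("The Investigator considers the abnormality clinically significant");
- the SAE definition is met;
- an intervention is required;
- the treatment-action condition, "The event results in an action taken with Sym015 (dose-reduction and/or withdrawal".

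**When a dose must be held.** Protocol 7.1.4.2 sets four criteria for giving the next dose. Two are plain laboratory limits: ANC above 1.0 x10^9/L and platelets above 60 x10^9/L. The other two concern ongoing AEs. If any criterion fails, "dosing of Sym015 must be delayed until the patient meets the above criteria".

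**What is reported.** Protocol 10.5.3 lists as a safety endpoint "AEs leading to dose-reductions, dose delays and permanent treatment cessation". Among the summary tables in 10.5.3.1 is "AEs leading to trial drug-interruption or dose-reduction".

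**Fatal PD.** Protocol 9.1.4 says that for deaths "the event(s) leading to the death should be recorded and reported as SAE(s) with the outcome" Fatal. Protocol 9.1.5 says PD is not captured as an SAE unless atypical, but adds that "PD may be reported as an SAE in the case of patient death". Section 9.1.2 has the matching note for AEs.

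**The concern.** The recording rule and the endpoint do not cover the same actions. The endpoint counts AEs behind reductions, delays and permanent cessation. The rule obliges sites to create a laboratory AE on treatment-action grounds only for reduction and withdrawal. A delay that the protocol itself imposes can then have no AE to which the endpoint can attach it.

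This affects the description of tolerability, namely how often cytopenias hold up dosing. It is a data-collection rule, so an analysis plan cannot repair it later: an AE that was never recorded cannot be tabulated. Any error from this gap goes in one direction, towards too few events.

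The note on fatal PD raises a smaller question of the same general sort. Because reporting is optional, two sites can handle the same PD death differently in the fatal-AE and SAE tables.

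**Working it through.** The protocol gives no figure to reproduce. The check sets the delay rule beside the reduction rule and then goes through the four conditions of 9.1.2.

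**Step 1. Where is a delay compulsory but a reduction not?**

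| Laboratory value | 7.1.4.2 | 7.1.4.3 |
|---|---|---|
| Platelets 25-60 x10^9/L, no clinically significant hemorrhage | Delay (not above 60) | No reduction (needs below 25, or Grade 3 with such hemorrhage) |
| ANC 0.5-1.0 x10^9/L, no febrile neutropenia | Delay (not above 1.0) | No reduction (needs febrile neutropenia, or below 0.5 for more than 5 days) |
| ANC below 0.5 x10^9/L for 5 days or less, no febrile neutropenia | Delay | No reduction |

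The reduction rule applies only to toxicities assessed as at least possibly related to Sym015. The two laboratory criteria for delay carry no such condition. For values judged unrelated, delay without reduction therefore extends beyond these ranges.

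**Step 2. Is the treatment-action condition met in these ranges?** No, because the only action is a delay. Withdrawal cannot stand in for delay: 6.3.1 uses it for stopping treatment. Sections 5.3.4 and 7.1.4 treat delay and reduction as separate actions, and 12.1 counts temporary interruptions as dose modifications in their own right.

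**Step 3. Do the other three conditions close the gap?**

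- *Serious:* not automatically. Under 9.2.3 even a Grade 4 laboratory value need not be reported as an SAE unless it meets a seriousness criterion.
- *Requires an intervention:* not if the count recovers untreated. Reading a held dose as an intervention would make the separate treatment-action condition redundant.
- *Clinically significant:* this is left to the investigator. The ANC and platelet criteria in 7.1.4.2 have no clinical-significance qualifier, so the delay is required whichever way that judgment falls.

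**Step 4. An example.** Exclusion criterion 13c in 6.2 admits a patient with platelets of 75 x10^9/L. The delay limit is reached after a fall of 75 - 60 = 15 x10^9/L, and 15/75 = 20%. Suppose the count is 58 on the next dosing day. The dose must be held, since 58 is not above 60. No reduction is triggered, since 58 is not below 25 and there is no hemorrhage. If the value is untreated, not serious and not called clinically significant, no AE is required, and the delay is absent from the outputs in 10.5.3 and 10.5.3.1.

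**Step 5. What remains in the database?** Section 12.1 sends interruptions of any cause, and local laboratory data, to the CRF. Section 10.5.3.2 lists all laboratory values with CTCAE grades for abnormal ones. Reading a delay as a temporary interruption, both the held dose and the count of 58 are retained. What is missing is the AE that joins them.

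**Step 6. Fatal PD.** Section 9.1.4 defines an SAE as a kind of AE and tells sites how to report events that lead to death. Sections 9.1.2 and 9.1.5 take typical PD out of the AE and SAE definitions, then permit it back in when the patient dies. The texts fit together as a general rule and an exception, but the permission gives no rule for when to use it. Section 5.1 expects 15 to 27 sites in Part 2 across three regions, so practice can differ.

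**The case against.** The strongest reply is that the gap is narrow and little is lost. The investigator would have to hold a scheduled dose for a value and at the same time regard it as not clinically significant. Section 8.2.9 requires results to be assessed before each dose, so that judgment is made at the visit in question. Two of the four dosing criteria already concern AEs, so those delays are linked to an AE from the start. The endpoint counts AEs as the protocol defines them and does not promise to count every delay. All analyses are descriptive, and neither primary endpoint is touched.

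Most of this stands and limits the point. It does not remove it: following 9.1.2 as written can still leave a mandated delay with no AE, and whether it does depends on individual judgment.

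Three stronger readings are tempting, and the documents do not support them.

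- A reader might infer that every delay caused only by an untreated, non-serious laboratory value is missed, or that the outputs are shown to be biased. Any of these values may still be recorded as clinically significant, so under-counting is possible but not demonstrated.
- A reader might infer that the safety monitoring committee cannot see these delays. Section 12.1 has it reviewing clinical and laboratory data, with dose modifications and local laboratory results among the data supplied.
- A reader might infer that 9.1.2 and 9.1.5 contradict 9.1.4 on fatal PD. Section 9.1.4 concerns events that are already AEs, and the PD text is a specific exception; the summary of changes for Amendment 4 (21.4) shows that it was introduced on purpose. Deaths are also captured through survival follow-up. What survives is the discretion in the notes, not a conflict.

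**Conclusion.** The point holds in a limited form. For neutrophil and platelet values in the ranges above, 7.1.4.2 requires a delay, but the treatment-action condition in 9.1.2 does not require an AE. When the other three conditions are also unmet, the outputs in 10.5.3 and 10.5.3.1 can under-count laboratory-driven delays.

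The size is unknown: the protocol gives no frequency for such values and no rate at which investigators call them clinically significant. The conclusion assumes that sites apply 9.1.2 as worded and that the bracketed actions are the full list, since they are not marked as examples. The delay and the laboratory value stay in the CRF. Sample size, the DLT rules and both primary endpoints are unaffected.

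The fatal-PD matter is secondary and minor. It is a possible inconsistency between sites in the fatal-AE and SAE tables, again with no count available.

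**What to change.** In 9.1.2, change the parenthesis to *(dose delay or interruption, dose-reduction and/or withdrawal)* and add a matching CRF completion note. This changes what is recorded, not any dosing threshold or patient management. The cost is a few more laboratory AEs and a slightly less favourable table of AEs leading to delay or interruption.

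Separately, reconcile 9.1.2, 9.1.4 and 9.1.5 to one uniform reporting rule for death from PD and remove the discretionary wording. Either direction would make the tables consistent: always a fatal SAE, or always recorded as cause of death and never as an AE or SAE unless atypical. The cost is a wording edit in each section.
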